3.9.3 Dietary Restrictions

Acalabrutinib can be taken with or without food. Because acalabrutinib is metabolized by CYP3A, subjects should be strongly cautioned against using herbal remedies or dietary supplements (in particular, St John's wort, which is a potent CYP3A inducer).

Otherwise subjects should maintain a normal diet unless modifications are required to manage an AE such as diarrhea, nausea, or vomiting.

3.9.4 Hepatitis B Virus Reactivation

Serious or life-threatening reactivation of viral hepatitis may occur in subjects treated with BTK inhibitor ([de Jésus Ngoma 2015](#)). Therefore, subjects who are anti-HBc positive, or have a known history of hepatitis B virus (HBV) infection, should be monitored every 3 months with a quantitative PCR test for HBV DNA. Regular monitoring (every 3 months) should continue until 12 months after last dose of acalabrutinib. Any subject with a rising viral load (above lower limit of detection) should discontinue acalabrutinib and have antiviral therapy instituted and a consultation with a physician with expertise in managing hepatitis B. Insufficient data exist regarding the safety of resuming acalabrutinib in subjects who develop HBV reactivation.

3.9.5 Progressive Multifocal Leukoencephalopathy

Serious or life-threatening occurrence of PML may occur in subjects treated with acalabrutinib. Increased risk of infections including PML may also occur in subjects treated with standard chemotherapy, including fludarabine and cyclophosphamide.

Signs and symptoms of PML may include cognitive and behavioral changes, language disturbances, visual disturbances, sensory deficits, weakness, and coordination and gait difficulties.

If PML is suspected, hold further study treatment (as applicable, based on risks in the Investigator Brochure or local prescribing information) until PML is excluded. A diagnostic evaluation may include (but is not limited to):

- *Neurologic consultation*
- *Brain MRI*
- *PCR analysis for John Cunningham or JC virus DNA in cerebrospinal fluid*

If PML is confirmed, permanently discontinue study treatment (as applicable, based on risks in the Investigator Brochure or local prescribing information).

3.9.6 Drug-Drug Interactions

Based on in vitro metabolism studies, acalabrutinib is not a strong direct inhibitor of CYP450 isoforms. Acalabrutinib directly inhibited CYP2C8, CYP2C9, and CYP3A/5 (for both midazolam 1'-hydroxylation and testosterone 6 β -hydroxylation) with IC₅₀ values of 37 μ M, 28 μ M, 69 μ M, and 57 μ M, respectively. There was little or no evidence of direct inhibition of CYP1A2, CYP2B6, 2C19, or CYP2D6 by acalabrutinib (IC₅₀ >100 μ M). Acalabrutinib is a weak metabolism-dependent inhibitor of CYP2C8, CYP2C9, and CYP3A/5, and inhibited CYP3A/5 in an irreversible manner. Based on these data, acalabrutinib is not expected to increase systemic exposure of coadministered CYP substrates, nonetheless, plasma concentration monitoring of narrow therapeutic index anticonvulsants will be undertaken in the Phase 1b portion of the study.

If a subject requires treatment with a moderate CYP3A inhibitor, decrease the acalabrutinib dose to 100 mg QD during concomitant administration with the moderate inhibitor.

Avoid coadministration of strong CYP3A inducers. If a subject requires treatment with a strong CYP3A inducer, increase the acalabrutinib dose to 200 mg BID during

concomitant administration with the strong inducer and return to recommended dose of 100 mg BID after stopping the strong CYP3A inducer.

Use of proton-pump inhibitors, H2 receptor antagonists, or antacids while taking acalabrutinib has the potential to decrease acalabrutinib exposure. If treatment with a gastric-acid reducing agent is required, consider using a H2-receptor antagonist (2 hours after acalabrutinib) or antacid (2 hours before or 2 hours after acalabrutinib). Avoid coadministration with proton-pump inhibitors.

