1.3.3 Drug-Drug Interaction Potential

For more detailed information on drug-drug interaction potential for acalabrutinib, refer to the Investigator Brochure. Please refer to [Section 3.9.6](#) for guidance on drugs that may cause drug-drug interactions.

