3.7 DOSING DELAYS AND MODIFICATIONS

Subjects should be followed closely for AEs or laboratory abnormalities that might indicate acalabrutinib-related toxicity. If a subject experiences an intolerable AE during the course of therapy, then acalabrutinib should be withheld, as necessary, until the AE resolves or stabilizes to an acceptable degree.

The actions in [Table 3-1](#) should be followed for the following toxicities:

- Grade 4 neutropenia (ANC <500/ μ L) for >7 days (neutrophil growth factors are permitted per American Society of Clinical Oncology (ASCO) guidelines [[Smith 2015](#)] and use must be recorded on the electronic case report form [eCRF])
- Grade 3 thrombocytopenia - in presence of significant bleeding
- Grade 4 thrombocytopenia
- Grade 3 or 4 nausea, vomiting, or diarrhea, if persistent despite optimal antiemetic and/or anti-diarrheal therapy
- Any other Grade 4 toxicity or unmanageable Grade 3 toxicity

Table 3-1. Drug Modification Actions for Acalabrutinib

Occurrence	Action
1 st	Hold acalabrutinib until recovery to Grade \leq 1 or baseline; may restart at original dose level (200 mg BID or 400 mg QD)
2 nd	Hold acalabrutinib until recovery to Grade \leq 1 or baseline; restart at one dose level lower (100 mg BID or 300 mg QD, respectively)
3 rd	Hold acalabrutinib until recovery to Grade \leq 1 or baseline; restart at one dose level lower (100 mg QD or 200 mg QD, respectively)
4 th	Discontinue acalabrutinib

BID=twice per day; QD=once per day.

Note: Under Amendment 2 of the protocol, the SAC observed that the response and disease-control rate observed in the 200-mg BID cohort were numerically higher than in the 400-mg QD cohort. Therefore, the 400-mg QD cohort was discontinued.

As appropriate, certain laboratory abnormalities may warrant more frequent monitoring (e.g., once per week) until abnormalities have recovered to Grade \leq 1. If acalabrutinib is reduced for apparent treatment-related toxicity, the dose need not be re-escalated, even if there is minimal or no toxicity with the reduced dose. However, if the subject tolerates a reduced dose of acalabrutinib for \geq 4 weeks, then the dose may be increased to the

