3.8.2 Prohibited or Restricted Concomitant Therapy

Subjects requiring EIAEDs that are strong CYP inducers (including carbamazepine, oxcarbazepine, phenytoin, fosphenytoin, phenobarbital, and primidone) cannot be enrolled to this study.

For subjects who are taking EIAEDs (e.g., carbamazepine or phenytoin), plasma concentration monitoring of low therapeutic index anticonvulsant cotherapy will be undertaken at weekly intervals during Cycle 1, and then monthly thereafter, or after a dose change during the study, according to the Schedule of Assessments ([Appendix 1](#)).

Note: Under Amendment 2 of the protocol, subjects requiring EIAEDs are not eligible for this study.

Any anticancer therapy including experimental therapy or radiotherapy for treating GBM is prohibited.

Warfarin or equivalent vitamin K antagonists (e.g., phenprocoumon) are prohibited.

The concomitant use of strong inhibitors of CYP3A (see [Appendix 3](#)) with acalabrutinib should be avoided when possible ([Section 3.9.6](#)). *If a subject requires short-term treatment with a strong CYP3A inhibitor (such as anti-infectives for up to 7 days), interrupt acalabrutinib treatment.*

Although acalabrutinib is not expected to increase exposure of coadministered therapeutics that are substrates for CYP isoforms, in vitro data revealed weak or metabolism-dependent inhibition of some CYP isoforms including CYP3A/5. For additional information on drugs with potential drug-drug interactions, refer to [Section 3.9.6](#).

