Appendix 3. Examples of Coadministered Drugs that Need Additional Consideration

Strong Inhibitors of CYP3A	Moderate Inhibitors of CYP3A
boceprevir	aprepitant
clarithromycin ^a	cimetidine
cobicistat ^a	ciprofloxacin
conivaptan ^a	clotrimazole
danoprevir and ritonavir ^b	crizotinib,
diltiazem ^a	cyclosporine
elvitegravir and ritonavir ^b	dronedarone ^a
grapefruit juice	erythromycin
idelalisib	fluconazole
indinavir and ritonavir ^b	fluvoxamine
itraconazole ^a	imatinib
ketoconazole,	tofisopam
lopinavir and ritonavir ^{a,b}	verapamil ^a
nefazodone	
nelfinavir ^a	
paritaprevir and ritonavir and (ombitasvir and/or dasabuvir) ^b	
posaconazole	
ritonavir ^{a, b}	
saquinavir and ritonavir ^{a, b}	
telaprevir ^a	
tipranavir and ritonavir ^{a, b}	
troleandomycin	
voriconazole	

Note: After discontinuation of the strong or moderate CYP3A inhibitor, wait 3 days before resuming ACP-319 or acalabrutinib.

- a. Inhibitor of P-glycoprotein.
- b. Ritonavir is usually given in combination with other anti-HIV or anti-HCV drugs in clinical practice. Caution should be used when extrapolating the observed effect of ritonavir alone to the effect of combination regimens on CYP3A activities.

Strong Inducers of CYP3A	Moderate Inducers of CYP3A
carbamazepine	bosentan
enzalutamide	efavirenz
mitotane	etravirine
phenytoin	modafinil
rifampin	
St. John's wort ^a	

- a. The effect of St. John's wort varies widely and is preparation-dependent.

P-gp Inhibitors	BCRP Inhibitors	Narrow Therapeutic Index P-gp Substrates
amiodarone	curcumin	digoxin
carvedilol	cyclosporine A	everolimus
clarithromycin	eltrombopag	sirolimus
dronedarone		
itraconazole		
lapatinib		
lopinavir and ritonavir		
propafenone		
quinidine		
ranolazine		
ritonavir		
saquinavir and ritonavir		
telaprevir		
tipranavir and ritonavir		
verapamil		

Source: FDA Drug Development and Drug Interactions: Table of Substrates, Inhibitors and Inducers. Web link Accessed 18 July 2018:
<http://www.fda.gov/Drugs/DevelopmentApprovalProcess/DevelopmentResources/DrugInteractionsLabeling/ucm093664.htm#inVivo>

Bile-Acid Sequestrants	Proton-Pump Inhibitors	H2-Receptor Antagonists

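### The Appendix 3 note has sites wait 3 days before resuming acalabrutinib after a moderate CYP3A inhibitor, but Section 3.9.6 never stops it

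*Protocol*

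**What the plan says.** Protocol Section 1.3.3 sends the reader to Section 3.9.6 "for guidance on drugs that may cause drug-drug interactions". The rules that bear on this point are:

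- **Moderate CYP3A inhibitor, Section 3.9.6:** "decrease the acalabrutinib dose to 100 mg QD during concomitant administration with the moderate inhibitor". No return time and no return dose are given.
- **Strong CYP3A inhibitor, Section 3.8.2:** "If a subject requires short-term treatment with a strong CYP3A inhibitor (such as anti-infectives for up to 7 days), interrupt acalabrutinib treatment".
- **Note under the CYP3A inhibitor table, Appendix 3:** "After discontinuation of the strong or moderate CYP3A inhibitor, wait 3 days before resuming ACP-319 or acalabrutinib".
- **Strong CYP3A inducer, Section 3.9.6:** raise acalabrutinib to 200 mg BID while the inducer is given, then "return to recommended dose of 100 mg BID after stopping the strong CYP3A inducer".

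The assigned dose in the continuing cohort is 200 mg BID (Section 3.0). Table 3-1 in Section 3.7 gives the reduced levels for toxicity: "restart at one dose level lower (100 mg BID or 300 mg QD, respectively" at the second occurrence and "restart at one dose level lower (100 mg QD or 200 mg QD, respectively" at the third.

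**The concern.** Section 3.9.6 does not list the moderate inhibitors. A site that needs to know whether a drug counts as one looks in Appendix 3 and finds the note directly under the table. The note puts strong and moderate inhibitors under one instruction that makes sense only if acalabrutinib was stopped. For a moderate inhibitor the body text keeps it going. The reference to ACP-319 suggests that the note was carried over from another protocol.

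Two sites could therefore dose the same subject differently and each point to protocol text. A site that takes the note to imply a hold would stop a drug that Section 3.9.6 says to continue. Section 3.7 cautions that even a 7-day interruption has been followed by transient worsening in CLL and that this may apply to glioblastoma.

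The inducer sentence is a plainer error in the same section. It cannot serve as a model for the missing return rule, because it names a dose that is not the study dose.

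**Working it through.** The plan states no figure for dosing around a moderate inhibitor, so there is none to reproduce. The check is direct arithmetic: mg per dose × doses per day × days.

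**Inputs.** Daily dose d is 400 mg at 200 mg BID (Section 3.0), 200 mg at 100 mg BID and 100 mg at 100 mg QD (both Table 3-1). The dose with a moderate inhibitor is 100 mg per day (Section 3.9.6). The wait is 3 days (Appendix 3).

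**Three readings of the 3 days after the inhibitor stops**

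- A: the reduction applies only during coadministration, so the prior dose returns at once. Dose = 3 × d.
- B: the note supplies the missing return time, so 100 mg QD continues for 3 more days. Dose = 3 × 100.
- C: the note implies that acalabrutinib was held. Dose = 0.

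| Dose level before the inhibitor | A | B | C |
|---|---|---|---|
| 200 mg BID | 3 × 400 = 1,200 mg | 3 × 100 = 300 mg | 0 mg |
| 100 mg BID | 3 × 200 = 600 mg | 300 mg | 0 mg |
| 100 mg QD | 3 × 100 = 300 mg | 300 mg | 0 mg |

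At 100 mg QD, readings A and B coincide.

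**Course plus 3 days at 200 mg BID.** The documents give no course length for moderate inhibitors, so the length L is an assumption. A = 100L + 1,200; B = 100(L + 3); C = 0.

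| Assumed L | A | B | C |
|---|---|---|---|
| 3 days | 1,500 mg | 600 mg | 0 mg |
| 7 days | 1,900 mg | 1,000 mg | 0 mg |
| 14 days | 2,600 mg | 1,700 mg | 0 mg |

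Under C, a 7-day course means 7 + 3 = 10 days off drug.

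**Relative dose intensity.** SAP Appendix 12.1 defines it as total dose over protocol-specified total dose. Assume a 28-day window, a 7-day course and a denominator of 28 × 400 = 11,200 mg:

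- A: (700 + 21 × 400) / 11,200 = 9,100 / 11,200 = 81%
- B: (1,000 + 18 × 400) / 11,200 = 8,200 / 11,200 = 73%
- C: (18 × 400) / 11,200 = 7,200 / 11,200 = 64%

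**Inducer sentence.** Taken literally, a subject at 200 mg BID goes from 400 to 200 mg per day once the inducer stops. That is the second-occurrence level of Table 3-1, reached without any toxicity. A subject already reduced to 100 mg QD would go up from 100 to 200 mg per day. Only a subject at 100 mg BID returns to the prior dose.

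**The case against.** The strongest reply is that the two texts cover different periods: Section 3.9.6 governs dosing while the inhibitor is given, and the note governs what follows. Section 3.9.6 never says that the full dose returns at once, so 1,200 mg is an inference from its wording. If the note fills that silence (reading B), both texts can be followed together. This stands. A reader might infer that the texts must differ by at least 1,200 against 300 mg. The documents do not support that, because the smallest conflict is zero.

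A reader might also infer that the note orders a hold during a moderate inhibitor. It does not. A hold would contradict the express instruction in Section 3.9.6, so reading C is the weaker one, and its course totals also rest on assumed lengths. The 10 days off drug should not be taken as demonstrated harm: Section 3.7 permits holds of up to 28 consecutive days for toxicity, and Section 3.10 provides for transient worsening during an interruption.

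Section 1.3.3 refers sites to the Investigator Brochure for more detail. It is not among the documents reviewed and may settle the return time. The milligram figures are nominal doses, not exposure.

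Cimetidine might be raised as a further conflict, since Section 3.9.6 advises sites to "consider using a H2-receptor antagonist (2 hours after acalabrutinib" and Appendix 3 lists cimetidine both as an H2-receptor antagonist and as a moderate inhibitor. The two rules can be applied together, so preferring another agent is a matter of choice and not a correction.

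What remains is that the note's reference to moderate inhibitors has no interruption to attach to, and no text in the protocol chooses among the readings.

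**Conclusion.** The point holds as a minor dosing-safety correction. The note does not fit the body text for moderate inhibitors and names a drug outside the study. In the 3 days after the inhibitor stops, a subject on 200 mg BID could be given 1,200 mg, 300 mg or 0 mg according to the reading. Under the harmonised reading there is no conflict, but the protocol does not state it. The 100 mg BID return after a strong inducer is a separate and clearer error.

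The reach is small. SAP Section 3.1 records that Phase 2 was not recommended, and neither document shows that anyone remains on drug. A reader might infer that the 24 treated subjects were dosed under this wording or that ORR was affected. The documents show neither. The SAP follows Amendment 2.0 of 21 March 2017, while Appendix 3 cites a source accessed on 18 July 2018, and use of moderate inhibitors is not reported.

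**What to change.** Make three edits to the protocol:

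1. **Appendix 3 note:** *After discontinuation of a strong CYP3A inhibitor for which acalabrutinib was interrupted (Section 3.8.2), wait 3 days before resuming acalabrutinib.* This removes the moderate inhibitors and ACP-319 and keeps the wait where an interruption exists.
2. **Section 3.9.6, moderate inhibitors:** *Decrease acalabrutinib to 100 mg QD during coadministration; do not interrupt it; return to the prior dose level 3 days after the last inhibitor dose.* Three days is the only interval that the protocol gives after an inhibitor stops. If the Investigator Brochure supports return on stopping the inhibitor, write that instead. Either will do, provided that only one is written.
3. **Section 3.9.6, strong inducers:** replace the return to 100 mg BID with *return to the dose level taken before the inducer*.

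Sections 3.7 and 3.8.2 and the SAP need no change. The cost is one note and two sentences, with no new data and no effect on sample size or endpoints. The benefit is limited to any subjects still on drug, including any on continued access.

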3.0 STUDY DESIGN

This Phase 1b/2, multicenter, open-label study is designed to evaluate the efficacy and safety of acalabrutinib in subjects with recurrent GBM who have progressed after 1 or 2 prior systemic treatment regimens. Subjects meeting the eligibility criteria for the study will be assigned 1:1 to one of the following cohorts:

Cohort 1: acalabrutinib 200 mg administered orally (PO) BID

Cohort 2: acalabrutinib 400 mg PO QD (see note below)

An interim safety and efficacy analysis will occur approximately 8 weeks (2 cycles) after the 12th subject has been enrolled in each cohort in the Phase 1b portion of the study. Enrollment in each cohort will be held after the 12th subject has been enrolled while the interim safety and efficacy results are reviewed by a Scientific Advisory Committee (SAC) in collaboration with the Safety Review Committee. If acceptable safety and efficacy (e.g., 2 or more of the 12 subjects [$\geq 16.7\%$] achieve a complete response ([remission] CR) or PR; additional criteria may be considered by the SAC) are observed in either cohort, the sponsor may choose to expand the study to a total of 72 subjects. The acalabrutinib dosage for the Phase 2 portion of the study will be based on available safety and efficacy data from the Phase 1b cohorts. Note: depending on the Phase 1b results, the SAC and the Safety Review Committee may recommend continued evaluation of both regimens in the Phase 2 portion of the study. The final analysis will occur 24 weeks after the last subject is enrolled to the study (see note below).

For the purpose of analyzing potential drug-drug interactions, each initial 12-subject cohort will be comprised of 8 subjects who do not require enzyme-inducing antiepileptic drugs (EIAEDs) that are strong cytochrome P450 (CYP) inducers (including carbamazepine, oxcarbazepine, phenytoin, fosphenytoin, phenobarbital, and primidone) and 4 subjects who do require such drugs (see note below).

Subjects will be treated until disease progression, unacceptable drug-related toxicity, death, the start of new anticancer therapy for GBM, consent withdrawal, or are lost to follow-up. All subjects will be evaluated for response using the RANO criteria ([Wen 2010; Appendix 2](#)).

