next higher dose level, at the discretion of the investigator. Such re-escalation may be particularly warranted if further evaluation reveals that the AE that led to the dose reduction was not treatment-related. However, the maximum dose of acalabrutinib is 200 mg BID or 400 mg QD for this protocol. Note: Under Amendment 2 of the protocol, the 400-mg QD cohort was discontinued.

The following action should be taken for a Grade ≥ 2 intracranial hemorrhage: If evidence of a Grade ≥ 2 intracranial hemorrhage is observed, then acalabrutinib should be withheld until the subject is clinically stable and the medical monitor must be notified.

Treatment with acalabrutinib should be withheld for any unmanageable, potentially study drug-related toxicity that is Grade ≥ 3 in severity. Any other clinically important events where dose delays may be considered appropriate by the investigator must be discussed with the medical monitor. Study drug may be withheld for a maximum of 28 consecutive days from expected dose due to toxicity. Study treatment should be discontinued in the event of a toxicity lasting >28 days, unless reviewed and approved by the medical monitor.

Note: Temporary withholding of acalabrutinib for as little as 7 days can cause a transient worsening of disease and/or of constitutional symptoms in CLL, which may also be applicable to glioblastoma. Refer to [Section 3.10](#) for more information on assessing disease progression under these circumstances.

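### Protocol Section 3.9.6 sets the dose after a strong CYP3A inducer at 100 mg BID, half the 200 mg BID assigned in this study

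*Protocol*

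**What the plan says.** Section 3.9.6 (Drug-Drug Interactions) opens its inducer rule with "Avoid coadministration of strong CYP3A inducers". For a subject who nevertheless needs one, it tells the site to "increase the acalabrutinib dose to 200 mg BID during" the co-treatment and afterwards to "return to recommended dose of 100 mg BID after stopping the strong CYP3A inducer".

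The study's own doses are set elsewhere:

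- Section 3.0 assigns Cohort 1 to "acalabrutinib 200 mg administered orally (PO) BID". Cohort 2 was assigned 400 mg QD and has been discontinued.
- Section 3.7 states that "the maximum dose of acalabrutinib is 200 mg BID or 400 mg QD for this protocol".
- Table 3-1 in Section 3.7 brings in 100 mg BID at the second occurrence of a listed toxicity: "restart at one dose level lower (100 mg BID or 300 mg QD, respectively").

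Sections 1.5 and 3.2 also mention doses from 100 to 200 mg BID, but only when describing the CLL study.

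**The concern.** The inducer rule assumes a study in which 100 mg BID is the standing dose and 200 mg BID is a temporary doubling. In this study 200 mg BID is both the standing dose and the maximum. A full-dose subject therefore has nothing to be increased to, and is then told to go back to a dose never received.

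What is at stake is dosing of individual subjects. Section 3.2 explains that the doses were picked to get as much drug as possible into the CNS, because brain penetration is expected to be low. A rule that halves the dose for no clinical reason works against that aim. I found no other text in the protocol that overrides the sentence.

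**Working it through.** The plan gives no figure to reproduce here. The check compares nominal daily doses.

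**Inputs**

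- Assigned doses: 200 mg BID (Cohort 1) and 400 mg QD (Cohort 2), Section 3.0.
- Dose during the inducer: 200 mg BID, Section 3.9.6.
- Dose after the inducer: 100 mg BID, Section 3.9.6.
- Ceiling: 200 mg BID or 400 mg QD, Section 3.7.
- Reduced level after a second toxicity in Cohort 1: 100 mg BID, Table 3-1.

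**Formula**

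Daily dose = mg per administration × administrations per day. Ratio = daily dose after the inducer ÷ daily dose before it.

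**Results if the sentence is followed literally**

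| Dose before inducer | Before (mg/day) | During (mg/day) | After (mg/day) | After ÷ before |
|---|---|---|---|---|
| 200 mg BID (assigned) | 2 × 200 = 400 | 2 × 200 = 400 | 2 × 100 = 200 | 200/400 = 0.50 |
| 400 mg QD (assigned, discontinued cohort) | 1 × 400 = 400 | 400 | 200 | 200/400 = 0.50 |
| 100 mg BID (after second toxicity) | 2 × 100 = 200 | 400 | 200 | 200/200 = 1.00 |

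For a subject on the assigned 200 mg BID, the step during the inducer is 400/400 = 1.0, so it is not an increase. A real increase would exceed the Section 3.7 maximum. The stated return dose is right for a subject who was already at 100 mg BID for toxicity. For either assigned dose it halves the daily amount.

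With the return dose corrected to the pre-inducer dose, the ratio is 400/400 = 1.0 at either assigned dose.

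**The case against.** The strongest reply is that the rule will hardly ever be used. Section 3.3.2 excludes subjects who need antiepileptics that are strong inducers, and Section 3.9.6 tells sites to avoid the class. The one subject recorded on such a drug was in Cohort 2 and has left the study (Section 3.2). SAP Section 3.1 adds that Phase 2 was not recommended. All of this stands and keeps the point small. It does not make the dose right. Section 3.9.6 gives dosing for the subject who does need an inducer, Appendix 3 lists rifampin among others, and Section 3.6 lets subjects who are benefiting stay on drug within this study.

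A second reply is that sites would notice. Section 3.5 refers dosing questions to Section 3.7, and one cannot go back to a dose never taken. That makes literal use less likely, but it relies on sites setting aside a written instruction.

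Some stronger readings are tempting, and the documents do not support them:

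- *Relative dose intensity would hide the halving.* A reader might infer that Section 3.9.6 makes 100 mg BID the protocol-specified dose in the denominator. However, SAP Section 12.1 bases the planned dose on days of exposure, which reads most naturally as days times the assigned dose. The SAP is also written to Amendment 2.0, while the protocol under review is later and lists Section 3.9.6 among its updated sections. Nothing shows that this sentence was in the version the SAP refers to.
- *At most 15 subjects are exposed.* SAP Table 1 shows 15 subjects enrolled in Cohort 1, but Cohort 2 (9 subjects) was also on 400 mg/day. Neither number counts those still on treatment under this text.
- *A definite cumulative shortfall.* Such a figure would borrow the Section 3.7 re-escalation provision, available "if the subject tolerates a reduced dose of acalabrutinib for" at least 4 weeks. That provision is written around reductions for toxicity, so the result would be an illustration, not an estimate.
- *A doubled dose as a main hazard.* A subject at 100 mg QD would go from 100 to 200 mg/day after the inducer. The arithmetic is right, but Table 3-1 reaches that level only at a third toxicity, and an inducer must then be needed as well. This remote case does not need a rule of its own to correct the return dose.

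**Conclusion.** The point holds as an internal inconsistency: the return dose in Section 3.9.6 is wrong as written for this study. Its size is a halving of the nominal daily dose, 400 to 200 mg, for a subject on either assigned dose, with no toxicity to justify it. The severity is minor.

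This rests on the sentence being applied literally, and it concerns nominal dose, not exposure. How many subjects took a strong inducer on treatment is not reported, and the entry and co-medication restrictions suggest few. The documents give no basis for claiming an effect on ORR, PFS or the safety summaries.

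The text may have been carried over from a study dosed at 100 mg BID. The summary of changes says that the listed sections were aligned with the Investigator Brochure and/or other sponsor protocols, and Appendix 3 mentions resuming ACP-319, which is not given here. That suggests the origin but does not prove it, and the conclusion does not depend on it.

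**What to change.** In Section 3.9.6, replace the return instruction with: *return to the dose the subject was receiving before the inducer (200 mg BID unless previously reduced for toxicity)*. Add that subjects already at 200 mg BID stay at that dose during the inducer, because it is the protocol maximum. This second statement only makes Sections 3.9.6 and 3.7 agree. The main clause would also cover anyone still on 400 mg QD.

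The cost is a wording correction made through a protocol amendment submitted to the IRB/IEC, as Section 7.8 requires, and a notice to sites. Sample size, data collection and the planned analyses do not change.

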3.2 RATIONALE FOR STUDY DESIGN AND DOSING REGIMEN

This Phase 1b/2, multicenter, open-label study is designed to evaluate the efficacy and safety of acalabrutinib in subjects with recurrent GBM who have progressed after 1 or 2 prior systemic treatment regimens. Acalabrutinib has been safely used to treat subjects with hematologic disorders, and 12 subjects in each cohort should be sufficient to preliminarily assess both safety and efficacy in subjects with GBM. The expansion phase (Phase 2 portion) should allow for further safety data and was designed to sufficiently power the study for determination of ORR (see [Section 5.1](#)).

The 200-mg BID and 400-mg QD dosages of acalabrutinib was selected to maximize CNS concentrations of acalabrutinib, given that relatively low brain penetration is expected due to transport by P-gp.

Additionally, as described in [Section 1.4](#), acalabrutinib is currently being evaluated in a Phase 1/2 study in subjects with CLL, Richter's syndrome, or prolymphocytic leukemia (ACE-CL-001). In this study, subjects have received oral dosages of 100 to 400 mg QD

and 100 to 200 mg BID of acalabrutinib. All tested dose levels have been well tolerated. No DLT has occurred at any dose level. Acalabrutinib 200 mg BID and 400 mg QD have been well tolerated by subjects with CLL (ACE-CL-001). See *the Acalabrutinib Investigator Brochure for details*. This study is exploring QD and BID regimens as the BTK resynthesis rate in target cells for this indication is unknown. Robust clinical responses have been observed.

Note, according to the original study design, subjects meeting the eligibility criteria for the study were to be assigned 1:1 (12 subjects per cohort) to either Cohort 1 (acalabrutinib 200 mg administered PO BID) or Cohort 2 (acalabrutinib 400 mg PO QD). Each cohort was to enroll 8 subjects who did not require EIAEDs) and 4 subjects who required these EIAEDs. However, EIAEDs are no longer considered the standard of care for patients with glioblastoma ([NCCN Guidelines 2016](#)). Therefore, these subjects have been difficult to enroll. As a result, the requirement for subjects on EIAEDs has been eliminated. Also, due to some response observed in the 200-mg BID group, and none observed in the 400-mg QD group, the SAC recommended the 400-mg QD cohort be discontinued. One patient on EIAEDs was enrolled into the 400-mg QD arm, was treated per protocol, and has exited the study due to disease progression.

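### Section 3.9.6 sends subjects to 100 mg BID after a strong CYP3A inducer stops, which is neither this study's assigned dose nor tied to the subject's Table 3-1 level

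*Protocol*

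**What the plan says.** Section 3.9.6 of the protocol first discourages the combination: "Avoid coadministration of strong CYP3A inducers". For a subject who nevertheless needs such a drug, the site is to "increase the acalabrutinib dose to 200 mg BID during" the period of combined use and afterwards "return to recommended dose of 100 mg BID after stopping the strong CYP3A inducer".

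Other sections describe the dose differently:

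- Section 3.0 assigns "Cohort 1: acalabrutinib 200 mg administered orally (PO) BID".
- Section 3.2 gives the reason: "The 200-mg BID and 400-mg QD dosages of acalabrutinib was selected to maximize CNS concentrations of acalabrutinib", because little of the drug is expected to reach the brain.
- Section 3.7 sets a ceiling: "the maximum dose of acalabrutinib is 200 mg BID or 400 mg QD for this protocol".
- Table 3-1 in Section 3.7 brings in 100 mg BID at the second qualifying toxicity: "restart at one dose level lower (100 mg BID or 300 mg QD, respectively". The third brings a Cohort 1 subject to 100 mg QD, and the fourth ends treatment.
- Section 3.7 allows a reduced dose to go up one level once it has been tolerated for at least 4 weeks, if the investigator so decides.

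Sections 1.3.3 and 3.8.2 send sites to 3.9.6 for interactions. Section 3.5 sends them to 3.7 for dose changes. Section 3.7 does not mention interactions, and nothing states which section governs.

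**The concern.** The phrase treats 100 mg BID as the standing dose, which it is not in this study. The sentence also fits badly with itself. An unreduced subject is told to increase to the dose already being taken, then to go back to a dose never taken.

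The instruction also takes no account of the level the subject held before the inducer. A site that applies it would move subjects in opposite directions. A subject without toxicity would lose half of a dose chosen for brain exposure. A subject reduced to 100 mg QD after three qualifying toxicities would end on a higher dose than before, although nothing in 3.9.6 asks about tolerance. What is at stake is the correct dosing of individual subjects.

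**Working it through.** The plan gives no figure of its own to reproduce. The check compares total daily dose before the inducer with the dose that 3.9.6 prescribes after it stops.

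**Inputs**

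- Cohort 1 levels from Table 3-1: 200 mg BID = 2 × 200 = 400 mg/day; 100 mg BID = 2 × 100 = 200 mg/day; 100 mg QD = 100 mg/day.
- Dose after the inducer from Section 3.9.6: 100 mg BID = 200 mg/day, for every subject.
- The 400 mg QD cohort was discontinued (Section 3.0) and is left out.

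**Formula:** ratio = 200 mg/day ÷ daily dose before the inducer.

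| Level before the inducer | mg/day before | mg/day after | Ratio |
|---|---|---|---|
| 200 mg BID (unreduced) | 400 | 200 | 200/400 = 0.5 |
| 100 mg BID (after second toxicity) | 200 | 200 | 200/200 = 1 |
| 100 mg QD (after third toxicity) | 100 | 200 | 200/100 = 2 |

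The instruction gives the right dose at one level of three, and there only by coincidence.

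**Comparison with Section 3.7.** Going from 100 mg QD to 100 mg BID is a rise of one level, which 3.7 could permit after 4 weeks of tolerance and at the investigator's discretion. Section 3.9.6 applies neither condition, so the two sections conflict for a subject who has not met them. For the unreduced subject, 3.7 offers no clear way back, because its re-escalation text is framed around reductions made for treatment-related toxicity and this reduction has no such cause.

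**How many subjects.** SAP Table 1 shows 15 Cohort 1 subjects, none on an enzyme-inducing antiepileptic drug. Exclusion criterion 11 bars subjects who need those drugs. SAP Section 3.1 reports that Phase 2 was not recommended, so no Phase 2 subjects are added. The instruction can still apply, because Appendix 3 lists strong inducers that are not antiepileptics, such as rifampin, and Sections 3.0 and 3.6 let subjects who benefit stay on treatment.

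**After the fix.** With return to the level held before the inducer, the ratios become 400/400, 200/200 and 100/100, that is 1 at every level.

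**The case against.** The strongest reply is that this is a latent slip in a rarely used sentence. Strong inducers are to be avoided, the commonest candidates are excluded at entry, and no Cohort 1 subject is shown to have received one. The doubled dose needs an unlikely chain: three qualifying toxicities, then a need for an inducer, then stopping it while still on acalabrutinib. An attentive investigator would probably notice. Sections 3.7 and 3.10 give room to delay dosing or to withdraw a subject in consultation with the medical monitor. All of this stands, and it is why the point is minor. It does not make the instruction correct: 3.9.6 is written for the subject who does need an inducer, and it prompts no check.

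It can also be said that nobody chose 100 mg BID as the return dose here. The amendment summary lists 3.9.6 among sections aligned with the Investigator Brochure or other sponsor protocols, and a note in Appendix 3 names ACP-319, which is not a drug in this study. Carried-over text is therefore a plausible origin. That is an inference, and the point does not depend on it.

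A reader might go further and infer that the dose during the inducer is also wrong, too low for an unreduced subject or too high for a reduced one. The documents do not support that. They give no exposure data on how far the dose offsets induction, and 200 mg BID is already the protocol maximum.

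**Conclusion.** The phrase is wrong as written: a minor internal inconsistency in a dosing instruction. Against the dose before the inducer, it gives half at 200 mg BID, the same at 100 mg BID and double at 100 mg QD. These ratios assume that the site follows 3.9.6 literally and that doses are compared as total mg per day. The conflict at 100 mg QD further assumes that the subject has not met the re-escalation conditions in 3.7.

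Three stronger readings should be resisted:

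- A reader might infer that subjects were misdosed or that the response rate was affected. The documents record no exposed Cohort 1 subject and give no basis for a study-level effect.
- A reader might infer a fixed loss of at least 4 weeks at half dose for an unreduced subject. The 4-week condition in 3.7 concerns reductions for treatment-related toxicity, so it does not clearly apply, and an investigator might restore the dose at once.
- A reader might extend the point to the moderate-inhibitor instruction in 3.9.6. That is a separate question, because Appendix 3 has its own note on waiting before acalabrutinib is resumed after such a drug.

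**What to change.** In Section 3.9.6, replace the return phrase with: *return to the dose level the subject was receiving before the inducer was started, or to the lower level required by Table 3-1 if a qualifying toxicity occurred during the inducer; any later increase follows Section 3.7*. The middle clause matters. Without it, a subject whose level was reduced for toxicity while on the inducer could be put back on the higher dose.

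Add a cross-reference from 3.7 to 3.9.6, so that a site using either section finds the other. Leave the instruction for the period of combined use as it is. The edit does not settle whether an unreduced subject needs a different dose during the inducer, and the documents do not allow that to be settled.

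The cost is one phrase and one cross-reference at the next amendment. No visits, procedures, subjects or treatment interruptions are added.
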